6.2 Secondary objectives

To evaluate the effect of LLG783 on symptomatic functional capacity after 3 months of treatment in subjects with PAD and intermittent claudication.

6.2.1 Variables

The secondary efficacy endpoint is the pain-free walking distance defined as the distance walked up to the point of onset of claudication symptoms as assessed by the 6MWT and will be used to evaluate symptomatic functional capacity of PAD subjects participating in this study.

Change from baseline in pain-free walking distance will also be derived. Baseline will be taken from the screening 6-minute walk test.

The exclusion rule of 6MWT defined in [Section 6.1.1](#) will also apply to pain-free walking distance.

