4.1 Inclusion criteria

Patients eligible for inclusion in this study must fulfill **all** of the following criteria:

1. Written informed consent (IC) must be obtained before any study assessment is performed.
2. Male and female patients 40 to 85 years of age (inclusive) at screening with clinical evidence of PAD and intermittent claudication (Fontaine stage II) ([Hardman et al 2014](#)). Intermittent claudication, as defined by pain with exertion in either leg (this may include atypical symptoms, e.g. fatigue, paresthesias, pallor, etc.) **AND** any **one** of the following:
 - a. resting ABI of 0.40-0.90 (inclusive) in at least one leg;
 - b. **OR** for patients with a resting ABI >0.90 but ≤ 1.0 , a decrease in ABI of $\geq 20\%$ with exercise (to be measured immediately following completion of 6MWT at screening) in at least one leg;
 - c. **OR** a decrease in ankle pressure ≥ 30 mmHg with exercise in at least one leg;
 - d. **OR** for patients with an ABI >0.90 , an abnormal toe-brachial index (TBI) <0.70 .

Note: documented values within 3 months of signing the informed consent are acceptable provided that there has been no peripheral revascularization in the interim.

3. On stable medical therapy for PAD and PAD symptoms, which may include statins, aspirin, and anti-platelet medications (as medically indicated) unless individually contraindicated, for at least 4 weeks prior to the screening visit.
4. Vital signs must be within the following ranges:
 - a. body temperature between 35.0-37.5°C
 - b. systolic blood pressure, 90-159 mm Hg
 - c. diastolic blood pressure, 50-99 mm Hg
 - d. pulse rate, 50 - 90 bpm

Refer to the SOM for guidance on collecting vital signs and repeated vital sign assessments in case screening vital signs are out-of-range.

5. Moderately impaired ambulatory function judged by the investigator to be due primarily to PAD and assessed by a maximum walk distance between 50 and 400 meters (inclusive of these values) at the screening 6MWT.

6. Able to communicate well with the investigator, to understand and comply with the requirements of the study.

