11.5.3 Pain-free walk distance

The change from baseline in pain-free walking distance will be analyzed in a similar way to MWD as described in [Section 11.4.2](#) and [Section 11.4.3](#).

Corporate Confidential Information

Corporate Confidential Information

Corporate Confidential Information

12 Ethical considerations

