1.1 Scope of document

The RAP documents contain detailed information to aid the production of Statistics & Programming input into the Clinical Study Report (CSR) for trial “**CLLG783X2201**”.

The Statistical analysis plan (SAP) describes the implementation of the statistical analysis planned in the protocol.

Tables, Figures, Listings (TFL) details the presentation of the data, including shells of summary tables, figures and listings, and Programming Datasets Specification (PDS) contains programming specifications e.g. for derived variables and derived datasets, to support the creation of CSR and IA outputs.

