6.1.3.1 Model checking procedures

Handling of missing values/censoring/discontinuations

The primary analysis will be based on all subjects with a baseline MWD and at least one post baseline MWD. Subjects who undergo any lower extremity vascular interventions (angioplasty, stenting, or bypass surgery) before the Week 16 efficacy assessment or subjects who drop out for other reasons before this assessment may be replaced to ensure 40 subjects complete this primary endpoint assessment. Data from such subjects will be included in the model for the primary analysis until the time of dropout or intervention; no imputation of the missing data will be performed for the primary analysis.

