6.2.3.1 Model checking procedures

Model checking procedures for pain-free walking distance will be the same as for primary analysis, refer to [Section 6.1.3.1](#).

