6.2.3.3 Sensitivity analyses

As sensitivity analyses, the same analysis described for the secondary analysis in [Section 6.2.3](#), will be performed using the last observation carried forward (LOCF) and worst observation carried forward (WOCF) approaches of imputation for missing pain-free walking distance.

Corporate Confidential Information

Corporate Confidential Information

Corporate Confidential Information

7 Statistical methods for safety and tolerability data

All subjects within the Safety analysis set will be included in the safety data analysis.

In case of dose adjustment occurring during the study, safety analyses will be performed by two analysis periods: pre-dose adjustment period and post-dose adjustment period. All subjects will be summarized by dose received during each period.

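### Does the SAP need to state a pain-free walking distance for six-minute walk tests that end without claudication symptoms?

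*SAP*

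**What the plan says.** SAP 6.2.1 describes pain-free walking distance as "defined as the distance walked up to the point of onset of claudication symptoms as assessed by the 6MWT", and adds: "Baseline will be taken from the screening 6-minute walk test". It carries over the four walk-test exclusions of SAP 6.1.1: recent narcotic use, the first test after a COPD exacerbation, tests after stenting or angioplasty, and a lap that is much too short.

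The analysis follows that of maximum walking distance (MWD). Protocol 11.5.3 says: "The change from baseline in pain-free walking distance will be analyzed in a similar way to MWD as described in" sections 11.4.2 and 11.4.3. SAP 6.2.3.1 says: "Model checking procedures for pain-free walking distance will be the same as for primary analysis". The section it points to, SAP 6.1.3.1, says: "The primary analysis will be based on all subjects with a baseline MWD and at least one post baseline MWD". SAP 6.2.3.3 adds last observation carried forward (LOCF) and "worst observation carried forward (WOCF) approaches of imputation for missing pain-free walking distance".

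Eligibility is set by total distance. Inclusion criterion 5 (Protocol 4.1) asks for moderately impaired walking, "assessed by a maximum walk distance between 50 and 400 meters (inclusive of these values) at the screening 6MWT". It does not ask that symptoms begin during that test.

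Two other documents bear on the derivation but are not available here. SAP 1.1 says that the Programming Datasets Specification "contains programming specifications e.g. for derived variables and derived datasets". Protocol 8.5.1 leaves the details of the walk test to the Site Operations Manual.

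**The concern.** The endpoint is defined by an event that may not happen. MWD exists for every test performed, because it is the total distance in six minutes. A point of symptom onset does not exist in a symptom-free walk. Such a walk can occur at screening, since onset there is not an entry requirement and atypical symptoms are accepted. It can also occur later, and there it is the best result the endpoint can show.

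If symptom-free tests were stored as missing, two things would follow. A patient with no onset at screening, or with none at any later visit, would lack a baseline or a post-baseline value and would leave the mixed model. LOCF and WOCF would also overwrite a symptom-free walk with an earlier or worse distance. Analyses meant to test robustness to missing data would then usually understate the effect.

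**Working it through.** **Step 1: what the text supports.** The two possible codings, set against the visible text:

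| Text | Total distance | Missing |
|---|---|---|
| Definition, SAP 6.2.1 | Natural reading: no onset, so the whole walk is pain-free | Not stated |
| Exclusions, SAP 6.1.1 as applied by 6.2.1 | A symptom-free test is not listed, so it stays in | Would act as a fifth, unlisted exclusion |
| Missing data, SAP 6.1.3.1 | Compatible | Missingness is described through dropout or intervention, not through completed tests |

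No sentence favours missing coding.

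**Step 2: scale.** The plan gives no visible figure to reproduce: the sample size text in the protocol is redacted and no SD for this endpoint is shown. With about 20 patients per arm, the half-width of the two-sided 80% interval is roughly

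1.2816 × SD × √(2/20) = 0.405 × SD.

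At an assumed SD of change of 80 m this is 0.405 × 80 ≈ 32 m.

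**Step 3: missing coding in the planned model.** Simulation inputs, all assumed:
- 20 patients per arm, four post-baseline visits, unstructured covariance, no dropout;
- latent onset delay of 50 m at Week 16, SD of change 80 m;
- no onset at screening in 0-15%, giving 5-25% (placebo) and 9-40% (LLG783) at Week 16;
- 24 settings with 300 trials each, so the Monte Carlo SE of power is about 0.03.

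| Quantity at Week 16 | Total distance | Missing |
|---|---|---|
| Treatment difference | 32-47 m | within -2.6 to +2.4 m of total distance |
| Patients analysed (average, of 40) | 40 | 32-40 |
| Standard error | reference | 0-24% larger |
| Power (lower 80% limit above 0) | 0.65-0.79 | 0.52-0.74 (1-13 points lower) |
| Rejection under no effect (2 settings, 600 trials each) | 0.10-0.11 | 0.09-0.13 |

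The largest average shift, 2.6 m, is 2.6/32 ≈ 8% of the half-width in Step 2.

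On average 0.1-3.7 placebo and 0.3-4.7 LLG783 patients leave the model. The ends of those ranges differ by 0.2 and 1.0 patients. At 15% without onset at screening, 0.15 × 20 = 3 patients per arm are expected to go for that reason alone. That is fixed before randomisation, so it costs precision but favours neither arm.

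**Step 4: a second, simpler simulation.** One post-baseline visit, analysis of covariance, 4,000 trials per setting. Assumed inputs: latent onset mean 130 or 180 m, SD 90 m, correlation 0.6; total distance mean 320 m, SD 60 m. Symptom-free tests were 4-10% at baseline, 5-11% later on placebo and 5-21% later on active.

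| Latent shift | Onset mean | All onsets known | Total distance | Missing | Total minus missing |
|---|---|---|---|---|---|
| 50 m | 130 m | 47.0 | 45.6 | 44.8 | 0.8 |
| 50 m | 180 m | 49.2 | 46.0 | 45.5 | 0.5 |
| 100 m | 130 m | 96.3 | 92.7 | 91.1 | 1.6 |
| 100 m | 180 m | 99.3 | 91.4 | 91.4 | 0.0 |

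With no shift, all estimates lie within 0.3 m of zero. The codings differ by under 2 m. Both fall short of the latent shift, by 1.4 m (47.0 - 45.6) to 7.9 m (99.3 - 91.4). That shortfall comes mainly from the six-minute limit, and a written coding rule would not remove it.

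**Step 5: carried-forward analyses.** In the settings of Step 3, missing coding makes LOCF 2-25% lower and WOCF 8-34% lower if baseline may be carried forward. If only post-baseline values are carried, the range is 11% lower to 3% higher. The SAP does not say that baseline is carried, so the larger losses need a second unstated choice on top of the first.

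**The case for a change.** The best case for a change is that the SAP is where such a rule belongs. It already lists test-level exclusions and extends them to this endpoint, and its carried-forward analyses depend on which values count as missing. Protocol 6.4 and SAP section 3 let the statistician, programmers and clinical team see unblinded results at interim analyses. A coding choice left open could therefore be made by people who know the treatment results. The remedy would be a few sentences and a table of counts.

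Part of this stands. The SAP is silent, and a written rule is tidier than an inferred one. The simulated shifts are also averages, so in a single trial of 40 the two codings could differ by more.

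The rest is weaker. Silence in the SAP does not show that the rule is unwritten, because the specification for derived variables and the walk-test manual cannot be seen. Writing the ordinary reading into the SAP would not change what a sensible analyst does. A count of symptom-free tests would describe the ceiling but not alter the analysis.

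A short rule is also less simple than it looks. If it covered every test that ends without claudication, a walk stopped early for breathlessness would count as an observed, low pain-free distance. A rule would have to separate six completed minutes from early stops for other reasons.

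**Conclusion.** No change to the plan is called for. SAP 6.2.1 leaves out a derivation detail that analysts would fill in the obvious way, with total distance for a walk completed without symptoms. The exclusion list is consistent with that reading and no text points to missing coding.

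The harm needs the less natural coding together with no-onset rates that the documents do not give. On those assumptions the average mixed-model estimate moves by less than 3 m. The remaining cost is 1-13 points of power, the lower end being within simulation error, and carried-forward results whose larger distortions need baseline to be carried as well. All of this concerns a secondary endpoint in a non-confirmatory study.

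The conclusion rests on total distance being the coding used. The programming specification or the Site Operations Manual would confirm it.

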6.2.2 Descriptive analyses

Secondary endpoint will be listed and summarized in an equivalent way as described in [Section 6.1.2](#).

6.2.3 Statistical model, assumptions and hypotheses

Secondary endpoint will be analyzed in an equivalent way as described in [Section 6.1.3](#).

6.2.3.1 Model checking procedures

Model checking procedures for pain-free walking distance will be the same as for primary analysis, refer to [Section 6.1.3.1](#).

6.2.3.2 Graphical presentation of results

Graphical presentation of results for pain-free walking distance will be the same as for primary analysis, refer to [Section 6.1.3.2](#).

6.2.3.3 Sensitivity analyses

As sensitivity analyses, the same analysis described for the secondary analysis in [Section 6.2.3](#), will be performed using the last observation carried forward (LOCF) and worst observation carried forward (WOCF) approaches of imputation for missing pain-free walking distance.

Corporate Confidential Information

Corporate Confidential Information

Corporate Confidential Information

7 Statistical methods for safety and tolerability data

All subjects within the Safety analysis set will be included in the safety data analysis.

In case of dose adjustment occurring during the study, safety analyses will be performed by two analysis periods: pre-dose adjustment period and post-dose adjustment period. All subjects will be summarized by dose received during each period.

7.1 Variables

Safety variables include adverse events, vital signs (body temperature, blood pressure, pulse rate, respiratory rate), height and weight, ECG intervals, laboratory measurements (hematology, clinical chemistry, urinalysis, coagulation panel), as well as subject demographics, baseline characteristics, and treatment information.

7.2 Descriptive analyses

Subject demographics and other baseline characteristics

All data for background and demographic variables will be listed by treatment group and subject. Summary statistics will be provided by treatment group.

Relevant medical history, current medical conditions, results of laboratory screens, drug tests and any other relevant information will be listed by treatment group and subject.

Treatment

Data for study drug administration and concomitant therapies will be listed by treatment group and subject.

Vital signs

All vital signs data will be listed by treatment, subject, and visit/time and if ranges are available abnormalities (and relevant orthostatic changes) will be flagged. Summary statistics will be provided by treatment and visit/time.

Height and weight

All height and weight and BMI data will be listed by treatment, subject, and visit, as part of the vital signs panel.

ECG evaluations

All ECG data will be listed by treatment, subject and visit/time, abnormalities will be flagged. Summary statistics will be provided by treatment and visit/time.

Clinical laboratory evaluations

All laboratory data will be listed by treatment, subject, and visit/time and if normal ranges are available abnormalities will be flagged. A separate listing is provided presenting all parameters in a subject with any abnormal values. Summary statistics will be provided by treatment and visit/time.

Adverse events

All information obtained on adverse events will be displayed by treatment and subject.

The number and percentage of subjects with adverse events will be tabulated by body system and preferred term with a breakdown by treatment. A subject with multiple adverse events within a body system is only counted once towards the total of this body system and treatment.

The number and percentage of subjects with adverse events by maximum severity of adverse events will be tabulated by body system and preferred term with a breakdown by treatment.

The number and percentage of subjects with adverse events classified as related to study drug will be tabulated by body system and preferred term with a breakdown by treatment.

ClinicalTrials.gov and EudraCT

For the legal requirements of ClinicalTrials.gov and EudraCT, two required tables on treatment emergent adverse events which are not serious adverse events with an incidence greater than 5% and on treatment emergent serious adverse events and SAE suspected to be related to study treatment will be provided by system organ class and preferred term on the safety set population and prepared internally by Novartis.

If for a same subject, several consecutive AEs (irrespective of study treatment causality, seriousness and severity) occurred with the same SOC and PT:

- a single occurrence will be counted if there is ≤ 1 day gap between the end date of the preceding AE and the start date of the consecutive AE
- more than one occurrence will be counted if there is > 1 day gap between the end date of the preceding AE and the start date of the consecutive AE.

For occurrence, the presence of at least one SAE / SAE suspected to be related to study treatment / non-SAE has to be checked in a block e.g., among AE's in a ≤ 1 day gap block, if at least one SAE is occurring, then one occurrence is calculated for that SAE.

The number of deaths resulting from SAEs suspected to be related to study treatment and SAEs irrespective of study treatment relationship will be provided by SOC and PT.

Other safety evaluations

Immunogenicity

All immunogenicity results will be listed by subject and visit/time. Summary statistics will be provided by treatment and visit/time.

7.3 Graphical presentation

Boxplots to visualize trends in longitudinal safety data (vitals, ECG, lab parameter) will be created.

8 Pharmacokinetic / pharmacodynamic relationships

All subjects within the PK/PD analysis set will be included in the PK/PD data analysis.

In case of dose adjustment occurring during the study, PK/PD analyses may be performed by two analysis periods: pre-dose adjustment period and post-dose adjustment period. All subjects will be summarized by dose received during each period.

Corporate Confidential Information

In addition, relationship between LLG783 concentration or an appropriate PK parameter and MWD may be explored in a graphical and/or modeling approach.

9 Statistical methods for biomarker data

Corporate Confidential Information

Corporate Confidential Information

Handling of LLOQ and ULOQ

Biomarker data are reported as concentration results, measured using a specific assay with a working range defined by the two limits: Lower limit of quantification (LLOQ) and Upper limit of quantification (ULOQ). Values which fall below the LLOQ or above the ULOQ are reported as $< \text{LLOQ} * \text{dilution factor}$ (dilution factor: if sample diluted and concentration measured still below LLOQ) and $> \text{ULOQ} * \text{dilution factor}$, respectively.

To ensure that biomarkers only have numerical values, censored values will be imputed as follows

- Values below the LLOQ are replaced by LLOQ/2.
- Values above the ULOQ are replaced by ULOQ.

Imputed values are used for summary statistics, inferential analyses and plots (with a special symbol). Values below LLOQ and values above ULOQ are shown as such in the listings. In the summary table, the frequency (n, %) of values below the LLOQ and above the ULOQ, respectively, will be included.

If the proportion of imputed data is more than 20% for any treatment group at any time point, a footnote is added to the summary statistics table stating that the proportion of values outside the limits of quantification is more than 20% for some treatment groups at some time points and that in such cases summary statistics may be heavily biased.

If the proportion of imputed data for a given biomarker, across all treatment groups and time points, is more than 50%, no summary statistics are provided and the data are only listed.

If the proportion of imputed data for a given biomarker, across all treatment groups and time points, is more than 30%, no inferential analysis will be performed.

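### SAP section 9 reports out-of-range biomarker results against dilution-adjusted limits but imputes them from the plain assay limits, so a diluted sample still above range is analysed below its known minimum

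*SAP*

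**What the plan says.** The text is in SAP section 9, under the heading on handling of LLOQ and ULOQ.

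- **What the limits are.** Biomarker concentrations are "measured using a specific assay with a working range defined by the two limits", LLOQ and ULOQ. These are properties of the assay, not of a sample.
- **How out-of-range results are reported.** "Values which fall below the LLOQ or above the ULOQ are reported as" less than LLOQ times the dilution factor and greater than ULOQ times the dilution factor, respectively. The factor is explained in a parenthesis for the low side only ("dilution factor: if sample diluted and concentration measured still below LLOQ"), but it appears in both expressions.
- **How they are imputed.** "Values below the LLOQ are replaced by LLOQ/2" and "Values above the ULOQ are replaced by ULOQ". Neither bullet mentions dilution.
- **Where the imputed numbers go.** "Imputed values are used for summary statistics, inferential analyses and plots". The results as reported are kept in the listings.
- **Safeguards.** More than 20% imputed in any group at any time point adds a footnote. More than 30% across all groups and time points stops inferential analysis. More than 50% leaves listings only.

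**The concern.** The subsection separates two quantities, the assay limit and the limit that applies to a given sample after dilution, and then imputes from the first when the data carry the second. Above range, that assigns a value which the laboratory result has excluded. This is more than a debatable convention for censored data: the number analysed is incompatible with the number reported.

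Two things follow if the rule is programmed as written. Ordering is lost, because a sample too high to read even after dilution is placed below one that dilution brought into range. Comparisons can also point the wrong way, because a rise from a measured high value to one beyond the diluted range appears as a fall. The biomarker summaries, models and plots would carry the error, and only the listings would show the true bound.

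**Working it through.** The plan states no figure on this point, so there is none to reproduce. The check is direct arithmetic on the rule.

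**Inputs.** From SAP section 9: the reported bounds LLOQ x DF and ULOQ x DF, and the imputed values LLOQ/2 and ULOQ. Assumed, because the documents do not give them: DF of 1, 2, 5, 10 or 50, and a working range of 1 to 100 units.

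**1. High side, single sample.** Known minimum = ULOQ x DF. Imputed = ULOQ. Ratio = ULOQ / (ULOQ x DF) = 1/DF.

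| DF | Known minimum | Imputed | Imputed / minimum |
|---|---|---|---|
| 1 | 100 | 100 | 100% |
| 2 | 200 | 100 | 50% |
| 5 | 500 | 100 | 20% |
| 10 | 1000 | 100 | 10% |
| 50 | 5000 | 100 | 2% |

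**2. High side, change from a measured value b.** True change is more than ULOQ x DF - b. Change as written is ULOQ - b. The first is positive and the second negative exactly when ULOQ < b < ULOQ x DF.

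| DF | b | True change | As written |
|---|---|---|---|
| 2 | 150 | more than 200 - 150 = +50 | 100 - 150 = -50 |
| 5 | 300 | more than 500 - 300 = +200 | 100 - 300 = -200 |
| 10 | 800 | more than 1000 - 800 = +200 | 100 - 800 = -700 |
| 10 | 50 | more than 1000 - 50 = +950 | 100 - 50 = +50 |

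In the last row b is below ULOQ, so the sign is kept and the rise is only understated.

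**3. Low side.** The result lies between 0 and LLOQ x DF. LLOQ/2 is inside that interval for every DF of 1 or more. At DF 10 the interval is 0 to 10, the imputed value is 0.5, and half of the reported limit would be 5. The two conventions differ by a factor of DF, but the data contradict neither.

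**4. Whether the percentage rules would catch it.** Take a hypothetical arm of 20 (about 40 patients, 1:1, Protocol section 3.1) at DF 10. Seventeen patients stay at 120. Three start at 300 and are later reported as above 1000.

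- Baseline mean: (17 x 120 + 3 x 300)/20 = 147.
- Later mean as written: (17 x 120 + 3 x 100)/20 = 117, a change of -30.
- Later mean using the reported bound: (17 x 120 + 3 x 1000)/20 = 252, a change of +105.

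The imputed share at that visit is 3/20 = 15%. If shares elsewhere are no higher, no threshold is crossed. The thresholds count imputed values and leave the values themselves unchanged.

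**The case against.** The best defence is that the bullets use shorthand. They follow directly on the reporting sentence, and a later sentence in the same subsection says that values beyond LLOQ or ULOQ are listed as such. There the plain terms must cover results reported with a dilution factor. The bullets could be read the same way, in which case the imputation already uses the reported limit. In addition, parts of section 9 ahead of this subsection are redacted, and SAP section 1.1 refers to a separate programming specification for derived variables, which is not among these documents. Either might settle the matter.

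This limits what can be claimed. One cannot say that the analysis will be wrong, only that the visible rule, taken at its word, gives a wrong value. It does not remove the point: the only visible definition of ULOQ is the assay's working range, and nothing visible redefines it.

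Three stronger readings are tempting, and the documents do not support them.

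- **That both ends are in error by a factor of DF.** Below range, LLOQ/2 is a possible value; half of the reported limit is a convention and not the truth.
- **That the comparison between arms is biased in a known direction.** That would need diluted, still out-of-range samples to be more frequent in one arm, and nothing in the documents says so. The visible text also does not confirm that biomarkers are analysed as change from baseline.
- **That the trial's main conclusions are at risk.** No biomarker appears among the visible primary or secondary objectives, the Week 16 criteria in SAP section 6.1.3 concern walking distance only, and PK has its own rule in SAP section 5.2.

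It is also fair that imputed points carry a special symbol in plots and are counted in the summary tables. That makes them visible but does not correct them.

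**Conclusion.** The point holds for samples with DF above 1 that remain above range. As written, they are analysed at 1/DF of their known minimum and below samples measured between ULOQ and ULOQ x DF. A change reverses sign only if the comparison value lies in that interval. On the low side there is an inconsistency of convention and no contradiction. At DF 1 there is no error.

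The size rests wholly on assumed dilution factors, and the frequency of affected samples is unknown, so the worked examples show what the rule can do and do not forecast its effect. The reach is confined to biomarker analyses in a non-confirmatory trial. Within that reach the rule should be corrected: under its literal reading it assigns a value that the result itself excludes, and no other visible provision repairs it.

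**What to change.** Replace the two imputation bullets with a rule tied to each sample's reported limit:

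- a result reported as above ULOQ x DF is replaced by ULOQ x DF;
- for consistency, a result reported as below LLOQ x DF is replaced by (LLOQ x DF)/2.

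Add that no above-range imputed value may be lower than the bound reported for that sample. With ULOQ 100 and DF 10, a baseline of 300 followed by a result above 1000 then gives 1000 - 300 = +700, a lower bound with the right sign, in place of 100 - 300 = -200.

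The cost is two lines of SAP text and, if the programs follow the literal wording, one programming change. No new data are needed, because the reported result already carries the limit. If the sponsor already intends dilution-adjusted limits, the change is to the wording only.
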